#### Potential Benefits of the Proposed Research to Research Participants and Others

While most participants should benefit from improved sleep and/or reduced insomnia complaints, as well as a comprehensive evaluation of their blood pressure and possible lowering thereof, there are no guaranteed benefits to the individual participant and no immediate benefits of the proposed research to others.

Information gathered from participants may help us to establish a link between sleep impairment and how insomnia has adverse effects on CVD risk. In our opinion, the anticipated benefits of this study outweigh the potential risks.

#### ANALYSIS PLAN

Data will be entered into a secure Microsoft Access database. Entry to the database is limited to key personnel and is password protected at the point of the workstation and the application. Standard double-entry and data checking approaches will be performed for all measures.

General Analytic Approach: Descriptive statistics will be performed on all study variables. In order to mitigate potential bias due to transient improvements in either sleep or BP dipping, we will utilize a 6-wk run-in phase after which participants will have their sleep efficiency and BP dipping markers re-assessed to ensure stability. Although we do not anticipate significant variation in either sleep or BP parameters during this pre-treatment phase, we will exclude participants who no longer meet inclusion criteria following the 6-wk run-in period. This practice has been shown to result in an increased magnitude of treatment improvements and therefore may improve the statistical power and potential precision of the proposed analyses. Markers of sleep efficiency and BP dipping collected after our run-in phase will therefore be used as our baseline assessment measures.

Regression-based analytic approaches will be used to examine associations between improved sleep efficiency, ABP indices, and mechanisms of CVD risk. In order to minimize potential confounding of treatment improvements due to either misdiagnosis or transient fluctuations in sleep, we will use assessments collected after the run-in period as our baseline time point. For our 6-week outcomes, improvements in sleep efficiency and ABP will be examined using simple regression analyses as detailed below. In contrast, our 6-month outcomes will be examined using repeated measures mixed models with an unstructured covariance matrix, using both 6-week and 6-month levels of the outcome modeled jointly. Incorporating both outcomes into a unified, mixed modeling approach will allow us to examine improvements in sleep as they associate with trajectories of BP dipping improvements and also allows for more robust handling of missing data.

For our primary aim examining improvements in sleep efficiency and ABP, we will focus on nighttime BP dipping as the outcome of interest with a prespecified significance level of  $P = .05$ . Because other ABP outcomes could plausibly be improved with CBT-I and will partially reflect improvements in nighttime dipping, we will conduct parallel analyses of nighttime average BP and 24-hour BP levels. Consistent with contemporary recommendations examining secondary outcome measures as supportive and/or explanatory, we will maintain a  $P = .05$  for all for secondary outcome measures. Patterns of missing data will be characterized using Rubin's criteria and managed accordingly using Harrell's multiple imputation (mult.impute) procedure in R. We will carefully examine all model assumptions and reparameterize as indicated. All analyses will be carried out using SAS (Cary, NC) or R (<http://cran.r-project.org/>) software.

**AIM 1:** Determine whether the circadian BP profile contributes CVD risk associated with poor sleep by evaluating whether it is modified by changes in sleep quality in men and women with hypertension and comorbid insomnia

**Hypothesis 1:** Improved sleep quality will be accompanied by: (i) enhanced nighttime BP dipping; (ii) lower average nighttime BP; (iii) lower average 24-hour BP.

**Analysis Plan:** General linear models will be used to examine the associations between improvements in sleep quality on improvements in BP dipping, controlling for age, gender, race, baseline sleep efficiency, baseline mean 24-hour BP, and pretreatment BP dipping, with post-treatment BP dipping as the criterion. Significance will a priori be set at  $P = .05$ . For follow-up analyses of 6-mo BP dipping, linear repeated measures mixed models will be examined in which 6-wk and 6-mo BP dipping both serve as outcome variables using the same covariates above. As an a priori explanatory analysis for our follow-up analyses, we will examine potential time X sleep efficiency interactions in order to examine the extent to which the association between sleep efficiency and BP dipping at six weeks differs from that at six-months. In addition, we will conduct an area under the curve analysis to examine overall associations that apply to both 6-wk and 6-mo in order to determine whether larger improvements in sleep are associated with larger improvements in BP outcomes in an overall sense. Because other ABP outcomes could plausibly be improved by CBT-I and also will reflect improved nighttime dipping, we will conduct parallel analyses of nighttime average BP and 24-hour BP levels.

**AIM 2:** Evaluate candidate mechanisms of CVD risk related to sleep quality in patients with hypertension and comorbid insomnia

**Hypothesis 2:** Improved sleep quality will be accompanied by: (i) reduced nighttime SNS activity; (ii) enhanced vascular endothelial function; (iii) reduced arterial stiffness, and; (iv) improved lipid profile.

**Analysis Plan:** General linear models will be used to examine the associations between improved sleep efficiency and improvements in mechanisms of CVD risk, controlling for age, gender, race, baseline sleep efficiency, and the pre-treatment (post run-in) level of the outcome. For our analyses of vascular endothelial function only, we also will adjust for baseline arterial diameter, consistent with our prior work. Follow-up analyses will follow the same approach as in Hypothesis 1, using linear repeated measures mixed models with 6-wk and 6-mo levels serving as the outcome variables.

Exploration of Mechanistic Relationships: For additional explanatory purposes in relation to our mechanistic conceptual model (Figure 1), we propose to conduct mediation analyses using the more commonly known Baron and Kenny approach as well as the newer MacArthur approach. By the MacArthur definition, the potential mediator must be during or post-treatment; therefore, changes in mechanisms of CVD risk occurring between baseline and 6-wk will be considered as potential mediators. The outcome then will be participants' post-treatment change in BP dipping, which will be assessed at 6-month follow-up. We will first fit a model to examine the relationship between changes in sleep efficiency and the mediator (C) (i.e., changes in mechanisms of CVD risk), as noted for Hypothesis 2. We will then fit a model examining the relationship between the mediator and post-treatment change in BP dipping. Finally, we will test for mediation using an extension of the Sobel first-order test, which examines the extent to which the associations between improved sleep efficiency and BP dipping are attributable to improvements in mechanisms of CVD risk. To fully understand these relationships, we will also investigate the MacArthur approach which is less restrictive in its assumptions, where improvements in BP dipping are attributable to improvements in mechanisms of CVD risk if there is evidence of a non-zero association between sleep efficiency and mechanisms of CVD risk, and either 1) mechanisms of CVD risk or 2) their interaction with changes in sleep efficiency also are non-zero.

Power and Sample Size Considerations: Our power estimates were derived from prior data assessing sleep efficiency and nighttime BP dipping among individuals with HTN using the following assumptions: an initial sample size of 150 individuals, attrition of 15%, an alpha of 0.05, and a correlation of  $r = 0.30$  between sleep efficiency and BP dipping. Using these assumptions, we will have 80% power to detect correlations of  $r \geq 0.25$  between improvements in sleep efficiency and BP outcomes, suggesting that we will have adequate power to test the proposed hypotheses. In a more conservative scenario for comparing the worst 1/3 of the sample in terms of sleep efficiency change to the best 1/3, and assuming 50 participants in each group, there is 0.85 power at the two-sided 0.05 significance level for the detectable effect size  $\theta = 0.6$  via the following equation:  $(n \text{ per group}) = 50 = 2 * (((1.96 + 1.04) / 0.6) ** 2)$ . In the present proposal, this corresponds to a difference of 2.2% in SBP dipping between high and low sleep efficiency groups.

Exploratory Analyses of Effect Modification: In addition to our formal analyses, we will conduct exploratory analyses of effect modification, which will be interpreted as hypothesis generating. Candidate markers for effect modification will include background and clinical characteristics, such as race, gender, baseline insomnia severity, baseline anxiety, and the presence of elevated depressive symptoms ( $BDI > 14$ ). Specifically, we will examine the interaction terms between these candidate moderators, changes in sleep efficiency and mechanisms of CVD risk using the same general linear modeling approach noted for Hypothesis 2.

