## Design & Procedures

The study design reflects our objective of identifying the mechanisms responsible for the increased risk of CVD among patients with hypertension and insomnia, and to determine if these mechanisms can be favorably altered by improving sleep quality. We propose to utilize a behavioral intervention to manipulate sleep quality in 150 adults with hypertension and comorbid insomnia. This mechanistic clinical trial design will assign all 150 participants to a 6-week CBT-I intervention, which has been shown to markedly improve sleep quality and promote consolidated sleep in approximately 60% of those treated; whereas approximately 40% do not respond to CBT-I. While CBT-I is generally effective, the anticipated wide-ranging treatment response will provide the prerequisite variability in sleep quality changes that will afford us the opportunity to help identify the mechanisms by which insomnia conveys CVD risk and by which improved sleep may lower CVD risk. Our design (see Figure 5 below) will include a 6-week run-in period, without treatment, to document the stability of sleep quality, ABP, and CVD risk mechanisms, which will serve as a basis of comparison following CBT-I treatment. Assessments will be performed at baseline, after the 6-week run-in period, after the subsequent 6-week CBT-I intervention, and at 6-month follow-up. Importantly, the study design will also establish whether these insomnia-driven CVD risk mechanisms are modifiable by CBT-I for participants who show improved sleep following treatment.

**Screening Assessments.** Initial telephone screening will be used to ascertain whether potential participants are likely to meet the study eligibility criteria, with a focus on previously observed clinic BPs and the presence of insomnia symptoms. For those who are likely eligible, the first of two screening sessions will be scheduled, at which informed consent will be first obtained. A medical history will be taken for eligible participants. For women, menopausal status will be documented by self-reported menstrual bleeding, using the criteria described by Tom and colleagues. Status categories are postmenopausal (natural or surgical), perimenopausal, and premenopausal. Menopausal status will be considered as a potential covariate in analytic models.

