## D.2. METHODOLOGICAL ISSUES

For this mechanistic study, we considered several alternative designs, including a cross-sectional observational study and a two-group randomized design. A cross-sectional design was rejected because differences in CVD risk factors between patients with poor sleep quality and good sleep quality could be due to other factors besides their sleep. However, because the study objective was mechanistic, with the (favorable) manipulation of sleep quality of primary interest as the independent variable, and

because CBT-I has emerged as the gold standard for treating insomnia, we could not uphold the principle of equipoise in a design that randomized participants to an intervention that would likely be markedly less effective in treating their insomnia (e.g., sleep hygiene, no treatment, wait-list control). Moreover, the study objective is not to ascertain the efficacy of CBT-I, so a randomized design and comparison group is not required. Indeed, with the efficacy of CBT-I at approximately 60%, the more ethically defensible design was considered to be that all participants should receive the CBT-I intervention, with a time-equivalent run-in phase serving as a within-participant control phase to help establish that more marked alterations in sleep quality (60%) should be attributed to the CBT-I intervention, with an estimated 40% showing minimal to clinically insignificant changes.

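### Excluding participants on the post-run-in visit and then using that visit as baseline biases mean change and the control phase, and leaves unclear what the 150 counts

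*Combined protocol and SAP*

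**What the plan says.** All references are to the combined protocol and SAP.

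- **Entry.** Selection of Subjects requires systolic BP of at least 130 mm Hg over two screening assessments, insomnia disorder, and age 30–60. Neither sleep efficiency nor BP dipping is a criterion. The office BP screening section enrols people after the second screening session, before the run-in.
- **Re-check.** Analysis Plan, General Analytic Approach: "we will exclude participants who no longer meet inclusion criteria following the 6-wk run-in period". The reason given is: "This practice has been shown to result in an increased magnitude of treatment improvements".
- **Baseline.** The same section: "Markers of sleep efficiency and BP dipping collected after our run-in phase will therefore be used as our baseline assessment measures".
- **Role of the run-in.** Design & Procedures describes it as documenting stability, "which will serve as a basis of comparison following CBT-I treatment". Section D.2, explaining why there is no randomised comparator, has everyone treated, "with a time-equivalent run-in phase serving as a within-participant control phase".
- **Numbers.** Design & Procedures: "This mechanistic clinical trial design will assign all 150 participants to a 6-week CBT-I intervention". The power section assumes "an initial sample size of 150 individuals, attrition of 15%, an alpha of 0.05" and claims 80% power for r of at least 0.25. Its tertile scenario uses 50 per group, which is the whole 150 without loss.

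The plan does not say which criteria are re-tested, how, or on how many readings. It gives no expected exclusion rate, does not say whether the 15% covers these exclusions, and does not say whether excluded participants' run-in data are kept.

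**The concern.** A single-arm trial that attributes change to treatment through an untreated lead-in needs that lead-in to be observed without a filter on its outcome. Here anyone whose BP or insomnia improves past the entry criterion without treatment is removed, while nobody is removed for what happens during CBT-I. Among those who remain, the run-in cannot show much improvement, whatever the truth.

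The same rule selects people whose post-run-in reading was high partly by chance. Because that reading is the baseline, the next one tends to fall with no treatment effect. The larger improvement that the plan offers as an advantage is then at least partly an artefact of selection.

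At stake are the mean changes from pre- to post-treatment and the comparison of the run-in with the CBT-I phase. A separate matter is the count: the design treats all 150, the analysis plan removes some before treatment, and the power section starts from 150 with 15% attrition.

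**Working it through.** **1. The plan's own power.** Inputs from the power section: 150 participants, 15% attrition, two-sided alpha 0.05, r = 0.25. Analysed n = 150 × 0.85 = 127.5, taken as 127. With the Fisher z approximation, power = Φ(atanh(r) × √(n − 3) − 1.96):

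- atanh(0.25) = 0.2554; 0.2554 × √124 = 2.844; Φ(2.844 − 1.96) = 0.81. The stated 80% is reproduced.
- n needed for 80%: ((1.96 + 0.8416)/0.2554)² + 3 = 123.3, so 124. The margin is 127 − 124 = 3 participants.

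**2. Power if exclusions come out of the 150 as well as the 15%.** The exclusion rate x is an assumption, since the documents give none. n = 150 × (1 − x) × 0.85, rounded down.

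| x | n | Power, r = 0.25 | Power, r = 0.30 |
|---|---|---|---|
| 0 | 127 | 0.81 | 0.93 |
| 5% | 121 | 0.79 | 0.92 |
| 10% | 114 | 0.77 | 0.90 |
| 20% | 102 | 0.72 | 0.87 |
| 30% | 89 | 0.66 | 0.82 |

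The 80% at r = 0.25 is lost once x exceeds about 3% (1 − 123.3/127.5). If 150 means those starting CBT-I, or the 15% includes run-in exclusions, the first row applies.

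**3. Regression to the mean in office systolic BP.** The documents give no variance components, so these are assumptions: each reading is a person's true level plus independent visit error, and nothing truly changes. Entry needs both screening values at 130 or above and BP not above 160. The first baseline, post-run-in and post-treatment visits follow, and a person is kept if the post-run-in value is at least 130. Five scenarios (mm Hg):

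| Mean / between-person SD / visit SD | Fail re-check | Run-in change, kept | CBT-I change, kept | First baseline to post-treatment, kept |
|---|---|---|---|---|
| 130 / 11 / 6 | 14.4% | +1.13 | −1.12 | 0.01 |
| 130 / 11 / 8 | 19.2% | +2.05 | −2.04 | 0.01 |
| 135 / 11 / 8 | 14.3% | +1.59 | −1.60 | −0.01 |
| 138 / 10 / 8 | 12.2% | +1.41 | −1.41 | −0.00 |
| 130 / 11 / 10 | 23.8% | +3.26 | −3.24 | 0.02 |

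With everyone kept, both changes are zero to within 0.02. Over a grid of 18 scenarios (mean 130–140, between-person SD 10–12, visit SD 6–10), 8–27% fail by chance, and the false rise and the false fall are each about 0.6–3.7 mm Hg. CBT-I change minus run-in change is therefore off by about twice that, roughly 1.3–7.4 mm Hg, in favour of CBT-I. The upper end belongs to the noisiest corner of the grid.

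**4. Does this reach the Aim 1 test?** The Aim 1 model regresses post-treatment dipping on sleep-efficiency improvement, adjusting for pre-treatment dipping, baseline sleep efficiency, baseline 24-hour BP and demographics. A large-sample simulation excluded on office systolic BP below 130 or an assumed insomnia score below 11 (34% removed) and adjusted for the three clinical baseline values:

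| True slope | Slope, all kept | Slope, exclusion applied |
|---|---|---|
| 0 | 0.008 | 0.008 |
| 0.2 | 0.129 | 0.129 |

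The shortfall from 0.2 comes from noise in the sleep measure and is the same either way. What moves is the mean: with a true slope of 0, mean dipping change goes from 0.00 to 0.25 points, and mean sleep-efficiency gain from 5.00 to 5.24 points.

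**The case against.** The strongest reply is that the primary analysis is an adjusted association, not a mean change. Selection is on neither dipping nor sleep efficiency, and the model adjusts for both at baseline. That stands. A reader might infer that the primary Aim 1 result is biased; the model as specified and the check above do not support that.

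The mm Hg figures are for office BP, which no hypothesis tests. The hypotheses concern ambulatory BP and other mechanisms, where the carry-over is smaller. No formal test of run-in against CBT-I is specified, and D.2 says that efficacy of CBT-I is not the objective. These points limit the size and reach of the harm. They do not remove it, because D.2 still relies on the run-in to attribute sleep change to CBT-I.

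Confirming persistent hypertension and insomnia before treatment is a recognisable enrichment aim, and the plan cites support for it that cannot be seen here. So removing the rule is partly a choice of study population. Taking the post-run-in visit as baseline is not a fault in itself; without the exclusion it reduces regression to the mean left over from screening.

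A reader might also infer that the stated power is definitely missed. The text does not settle this: enrolment before the run-in and the power section's description of the 150 as the starting sample point one way, while the statement that all 150 are assigned to CBT-I can be read the other way. At the power section's assumed r = 0.30, power stays at 0.82 even with 30% removed. Finally, a reader might infer that the exclusion narrows the spread of sleep change that the design depends on. Nothing in the documents shows this.

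**Conclusion.** The concern holds for mean changes and for the control phase. Excluding on the post-run-in visit and using it as baseline makes the run-in look stable or worse among those kept, and inflates the mean change over CBT-I. For office systolic BP the false shift is about 0.6–3.7 mm Hg in each phase, with 8–27% removed by chance. This assumes the variance ranges above, a single-visit re-check at 130 mm Hg, and no true change. Ambulatory measures carry a fraction of it, about 0.25 points for dipping in one illustrative set-up. The adjusted Aim 1 slope is not materially biased.

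The power point is conditional. If exclusions come out of the 150 in addition to the 15% attrition, power at r = 0.25 falls to 0.77 with 10% removed and 0.72 with 20%. Otherwise the stated 80% stands. Design & Procedures, the General Analytic Approach and the power section have to be reconciled.

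**What to change.** **Preferred.** Keep everyone enrolled in the analysis whatever their post-run-in values, and report the subset still eligible after the run-in as a sensitivity analysis. The post-run-in visit can then remain the baseline.

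**If the exclusion is kept:**

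- State which criteria are re-tested, how, and on how many readings.
- Report the number removed, and report run-in change for all enrolled, including those removed.
- Take pre-treatment values for mean pre-post and run-in versus CBT-I contrasts from the first baseline, a visit not used for the re-check. In the scenarios above this leaves no bias even with the exclusion. That change spans the run-in as well as CBT-I, so it should be read beside the run-in change in all enrolled.
- Say whether 150 counts those entering the run-in or those starting CBT-I, and whether the 15% includes run-in exclusions. If 150 counts those entering, restate the power, or enrol 150/(1 − x): 167, 188 or 215 for x of 10%, 20% or 30%.

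In either case, stop presenting the larger improvement as a gain without saying that selection contributes to it.

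**Cost.** Mostly wording. Mean improvement will look slightly smaller. If the exclusion is dropped, a non-trivial share of participants with less room to improve stays in (about 8–27% under the assumptions), which changes the population analysed. If it is kept and 150 must start CBT-I, enrolment rises.

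### The run-in is presented as the study's within-participant control, but no inferential analysis uses it and first-baseline sleep efficiency and dipping enter no model

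*Combined protocol and SAP*

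**What the plan says.** All references are to the combined protocol and SAP.

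- **Design & Procedures** includes the untreated run-in "to document the stability of sleep quality, ABP, and CVD risk mechanisms, which will serve as a basis of comparison following CBT-I treatment".
- **D.2. Methodological Issues** explains why there is no randomised comparator. It prefers a design in which "all participants should receive the CBT-I intervention, with a time-equivalent run-in phase serving as a within-participant control phase", to help credit the larger sleep changes to CBT-I. It also says that the efficacy of CBT-I is not the study objective.
- **Analysis Plan, General Analytic Approach** gives the run-in three uses: re-assessing sleep efficiency and dipping for stability (no statistic or threshold given), excluding participants who no longer meet inclusion criteria, and supplying the baseline: "Markers of sleep efficiency and BP dipping collected after our run-in phase will therefore be used as our baseline assessment measures". Descriptive statistics are promised for all variables.
- **Analysis Plan, AIM 1** regresses post-treatment dipping on improvement in sleep, "controlling for age, gender, race, baseline sleep efficiency, baseline mean 24-hour BP, and pretreatment BP dipping". The follow-up mixed model takes the 6-week and 6-month values as outcomes with the same covariates. **AIM 2** follows the same pattern with the post-run-in level of each outcome.
- **C.5** opens by saying that its assessments are made at all four visits. Its own subsections then limit urine collection to before and after CBT-I, and pulse wave velocity and echocardiogram to pre-CBT-I and 6 months.

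**The concern.** The design sections ask the run-in to show what happens without treatment. The analysis sections never make that comparison. Followed exactly, the plan produces an association between two changes over the same treated interval, with no formal statement of how much sleep efficiency or dipping moved, or moved together, over an equal untreated interval already measured in the same people.

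Untreated co-movement is plausible. Sleep logs help set the actigraphy in-bed window (C.4) and also define the nighttime BP window (C.5), so an error in the logs can shift both variables. At stake is the attribution of change to CBT-I and, secondarily, some precision in the primary model.

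**Working it through.** **1. The plan's own figures.** Inputs from Power and Sample Size Considerations: "an initial sample size of 150 individuals, attrition of 15%, an alpha of 0.05". The section's assumed r for the two measures is 0.30.

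- Evaluable n = 150 × 0.85 = 127.5, taken as 127.
- The plan states "we will have 80% power to detect correlations of" 0.25 or more. Fisher z: power = Φ(atanh(0.25) × √124 − 1.96) = Φ(2.844 − 1.960) = 0.812. The smallest r with 80% power is 0.246.
- The tertile scenario says "there is 0.85 power at the two-sided 0.05 significance level for the detectable effect size" of 0.6. Check: 2 × ((1.96 + 1.04)/0.6)² = 50 per group, power 0.851.

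Both reproduce. Neither concerns a run-in contrast.

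**2. Where each visit enters a model.**

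| Analysis | First baseline | Post-run-in | Post-CBT-I | 6 months |
|---|---|---|---|---|
| Aim 1 and Aim 2 general linear models | no | covariate | outcome | no |
| Follow-up mixed models | no | covariate | outcome | outcome |
| Mediation | no | start of change | mediator | outcome |

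**3. Precision from adding the first baseline.** Let a be the correlation between the first baseline and the post-run-in value, b that of the post-run-in value with the outcome, and c that of the first baseline with the outcome. With variances scaled to 1:

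- one baseline: residual variance = 1 − b²
- two baselines: residual variance = 1 − (b² + c² − 2abc)/(1 − a²)

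The documents give none of these correlations. All values below are assumptions.

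| Pattern | One baseline | Two baselines | Reduction |
|---|---|---|---|
| AR(1) decay, c = ab | 1 − b² | 1 − b² | 0% |
| a = b = 0.6, c = 0.5 | 0.640 | 0.609 | about 5% |
| Exchangeable, 0.5 | 0.750 | 0.667 | 11% |
| Exchangeable, 0.6 | 0.640 | 0.550 | 14% |
| Exchangeable, 0.7 | 0.510 | 0.424 | 17% |

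At 11% and 17%, 127 participants act like 127 × 0.750/0.667 = 143 and 127 × 0.510/0.424 = 153, and power at r = 0.25 rises from 0.81 to about 0.85 and 0.88. Under AR(1) nothing is gained and two degrees of freedom are spent: Φ(atanh(0.25) × √122 − 1.96) = 0.805 against 0.812. These figures ignore the other covariates already in the model, which could absorb part of the gain.

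**4. Feasibility of a run-in versus CBT-I contrast.** Define D = (post-CBT-I − post-run-in) − (post-run-in − first baseline). With equal variances and a common correlation ρ:

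- Var(D) = 6(1 − ρ)SD²
- simple pre-post change: 2(1 − ρ)SD², so D has three times the variance.

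The SD for dipping is inferred from the tertile scenario, where 2.2 points equal an effect size of 0.6: 2.2/0.6 = 3.67. The mean detectable with 80% power at n = 127 is (1.96 + 0.84) × 3.67 × √(6(1 − ρ)/127), or with 2(1 − ρ) for a simple change:

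| ρ (assumed) | D, dipping points | Simple change |
|---|---|---|
| 0.3 | 1.87 | 1.08 |
| 0.5 | 1.58 | 0.91 |
| 0.7 | 1.22 | 0.71 |
| 0.8 | 1.00 | 0.58 |

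**The case against.** The strongest reply is that the primary question is whether larger sleep gains go with larger dipping gains. That analysis is specified, and D.2 disclaims efficacy. D.2 ties the control phase to attributing sleep change, not BP or vascular change, and Design & Procedures speaks of mechanisms being modifiable in participants whose sleep improves. This stands as far as the primary model goes: the missing contrast does not invalidate it. It does not remove the gap, because the attribution of sleep change and the promised basis of comparison still have no matching analysis.

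Other points that stand:

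- The post-run-in baseline is a sensible guard against regression to the mean and should be kept.
- C.5 regards a single successful 24-hour recording as adequate. A second baseline covariate is therefore an efficiency option, not the repair of an error.
- A sleep–dipping association during the run-in could reflect the hypothesised mechanism or shared confounding. The plan also expects little movement in that period, so the estimate would be imprecise.
- The plan tests every secondary outcome at P = .05, so a long list of new formal contrasts would add unadjusted tests.

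A reader might infer that the run-in data are unused or thrown away. The documents do not support that: descriptive statistics, the stability re-check, the exclusion rule and the re-set baseline all draw on them. Nor can one infer that a complete first baseline exists for every mechanism, given the visit limits on urine, pulse wave velocity and echocardiogram.

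**Conclusion.** The concern holds in this form: the run-in is offered as the within-participant control, yet no inferential analysis uses it as one, and first-baseline sleep efficiency and dipping enter no model. It should be corrected before analysis, but it does not undermine the planned association or the stated power.

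The precision gain is uncertain: about 0% under AR(1) decay and 11–17% with exchangeable visits at ρ of 0.5–0.7. A reader might take the upper figures as the expected benefit, but the documents contain no visit-to-visit correlation to support that. The contrast on dipping could detect mean differences of about 1.0–1.9 points, for ρ between 0.8 and 0.3, an SD of 3.67 inferred from the power section, and complete data on 127. It controls for time and repeat measurement and does not replace randomisation.

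**What to change.** 1. **Covariates.** Keep the post-run-in value as baseline. Add the first-baseline values of dipping and of sleep efficiency to the primary general linear model and the 6-month mixed model. Cost: two degrees of freedom.
2. **Contrast.** Prespecify D as a supportive analysis for sleep efficiency and SBP dipping, and report it descriptively for other outcomes measured at all four visits. Fit it in a likelihood-based mixed model that includes everyone with run-in data, including those excluded after the run-in. State that the exclusion selects on the post-run-in visit, which both intervals share. The exclusion rule itself then need not change. Cost: D has three times the variance of a simple pre-post change under equal correlations.
3. **Association over the run-in.** Report the association of sleep-efficiency change with dipping change over the run-in beside the CBT-I-interval estimate, labelled as descriptive context and not as a test separating mechanism from confounding.
4. **Reconcile visits.** Bring the four-visit statement opening C.5 into line with the urine, pulse wave velocity and echocardiogram subsections, so that it is clear which outcomes can enter items 1–3.

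Overall cost: SAP wording and modest extra analysis. The sleep efficiency and dipping data are already planned at all four visits.
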